4.2 SCIENTIFIC RATIONALE FOR STUDY DESIGN

This Phase 2 study will explore the activity of etokimab in adult subjects with moderate to severe CRSwNP. Etokimab is a highly effective inhibitor of IL-33, a cytokine that is considered to drive the pathogenic cascade in asthma, AD, and CRSwNP. Interleukin-33 directly affects eosinophil counts and function by acting on the early phases of the atopic immune response, which is upstream of current asthma treatments with clinically validated targets such as IL-5, IL-4, and IL-13. The possibility to influence complementary and synergistic pathways involved in CRSwNP pathogenesis may provide a therapeutic improvement compared to the inhibition of single downstream pathways. This study will explore the effects of repeat doses of etokimab, administered SC over a 16-week treatment period, compared to placebo on validated endpoints, such as the NPS and SNOT-22.

4.3 JUSTIFICATION FOR DOSE

Data from the etokimab Phase 1 (ANB020-001) and Phase 2a (ANB020-002) studies are the basis for the selection of the dose of etokimab for the current study. The dose range of etokimab selected for this study has been used safely in study ANB020-001. Etokimab pharmacodynamic activity, measured as inhibition of ex-vivo IL-33 stimulated INF- γ production, can be inferred from the correlation with PK data. All of the selected dose levels of etokimab are predicted to induce full IL-33 inhibition within 2 days for at least 9 to 10 days after dosing. The administration of etokimab loading doses will allow systemic concentrations to reach serum concentrations sustaining more than 95% IL-33 inhibition faster, potentially reducing the time to onset of clinical effect. Data from the Phase 2a study show a clinical response 1 week after etokimab administration (300 mg IV), and the dose was found to be safe and well tolerated. One month after etokimab administration, the average EASI score reduction was 61% and the average pruritus reduction was 32% relative to baseline. Sustained clinical response was observed after 2 months after etokimab administration.

4.4 END OF STUDY DEFINITION

A subject is considered to have completed the study if he or she has completed all scheduled study visits, including the last visit or the last scheduled procedure, as shown in the Schedule of Activities (SoA), Section 1.3.

The end of the study is defined as the date of the last visit or procedure of the last subject in the study.

5 STUDY POPULATION

5.1 INCLUSION CRITERIA

Subjects must meet all of the following criteria in order to be eligible to participate in this study:

- 1. Male or female, aged 18 to 70 years at the time of consent.
- 2. Present with a minimum bilateral total NPS of 4 out of 8 (maximum score), with minimum score of 1 in each nostril, despite completion of a prior INCS treatment at least 8 weeks before Screening.
- 3. Present with at least 2 of the following symptoms prior to Screening:
 - a. Nasal blockade/obstruction
 - b. Nasal congestion
 - c. Nasal discharge (anterior/posterior nasal drip)
 - d. Facial pain/pressure, and
 - e. Reduction in or loss of smell
- 4. Body mass index (BMI) of 18 to 42 kg/m² (inclusive) and total body weight > 50 kg (110 lb).
- 5. Agrees to the following conditions regarding contraception and pregnancy:
 - a. A male subject must agree to use contraception as detailed in the protocol during the treatment period and for at least 3 months after the last dose of study treatment and refrain from donating sperm during this period.
 - A female subject of child bearing potential must have a negative serum pregnancy test (β-human chorionic gonadotropin) at Screening and a negative urine pregnancy test at Baseline (Day 1), is not lactating, and at least one of the following conditions applies:
 - i. Not a WOCBP as defined in the protocol, OR
 - ii. A WOCBP who agrees to follow the contraceptive guidance in the protocol during the treatment period and for at least 3 months after receiving the last dose of study treatment. The female subject's selected form of contraception must be effective by the time the female subject enters into the study (eg, hormonal contraception should be initiated at least 28 days before Day 1).
- 6. Screening laboratory values must meet the following criteria:
 - a. Aspartate aminotransferase (AST) and alanine aminotransferase (ALT) levels \leq 3 x ULN
 - b. Total bilirubin \leq 1.5 x ULN
 - c. Albumin \geq 3 g/dL lipase \leq 1.5 ULN (if collected)

If a subject has liver function tests (LFTs) within normal and defined limits at Screening and meets all other inclusion criteria at Screening and baseline, the subject can be dosed.

- 7. Capable of giving signed informed consent and understanding the requirements and restrictions listed in the ICF.
- 8. Subject must use MFNS as provided by the Sponsor and be approximately 80% compliant during the screening period through Day 1.
- 9. Willing to and capable of complying with the study protocol requirements.
- 10. Able to read and to understand the study procedures and have the ability to communicate meaningfully with the Investigator and staff.
- 11. Confirmation of completion of 1 week of daily NPIF recordings (twice daily) on Day 1, prior to randomization. (A minimum of approximately 5 days must be completed of the 7 consecutive days requested).

5.2 EXCLUSION CRITERIA

Subjects are excluded from the study if any of the following criteria apply:

- 1. Prior exposure to etokimab.
- 2. SNOT-22 score < 15 at Screening.
- 3. Use of other investigational drugs or prohibited therapy for this study within 8 weeks before screening or 5 half-lives, whichever is longer:
 - a) Have required an increase of OCS or INCS drops within the 2 months before screening or are scheduled to receive OCS during the study period for another condition
 - b) Have undergone any previous monoclonal antibody (mAb) or immunosuppressive treatment
 - c) Leukotriene antagonists/modifiers for subjects who were not on a continuous treatment for ≥ 30 days prior to Screening
- 4. Have a documented history of aspirin-exacerbated respiratory disease (AERD) diagnosis as confirmed by a medical provider with an oral aspirin challenge.
- 5. Have concomitant medical condition(s) that may interfere with the Investigator's ability to evaluate the subject's response to the investigational product (IP).
- 6. Have experienced a severe life-threatening anaphylactic reaction to human, humanized, chimeric, or murine monoclonal antibodies.
- 7. Have participated in any interventional study for the treatment of CRSwNP in the 3 months before Screening.
- 8. Have received high dose systemic corticosteroids (equivalent to > 15 mg/day prednisone), prolonged nonsteroidal, immunosuppressant, or immunomodulating treatments within 8 weeks before Screening.

- 9. Have received treatment with biologics such as dupilumab, mepolizumab, or omalizumab within 12 weeks or 5 half-lives (5 $T_{1/2}$), whichever is longer, before Screening.
- 10. Clinically significant abnormal ECG assessment at Screening (any abnormality that the Investigator believes is not safe for study participation).
- 11. History of ischemic cardiovascular disease(s) or cerebrovascular event within 1 year of Screening.
- 12. Have received any systemic antibiotic treatment within 4 weeks before Screening.
- 13. Have a history of hypersensitivity or allergic reactions to economic accomponent of the etokimab formulation or the inactive ingredients (excipients).
- 14. If female, is pregnant or lactating, or intends to become pregnant during the study period.
- 15. Current smokers or former smokers with a smoking history of ≥10 pack-years [(number of cigarettes per day/20) × number of years smoked]. A former smoker is defined as a subject who quit smoking at least 2 months prior to screening visit. This includes electronic cigarettes and vaping. Subjects who smoke medicinal marijuana can be enrolled at the Investigator's discretion (conversion to edible forms of marijuana is preferred). Occasional smoking is permitted at the discretion of the Investigator (eg, cigar or pipe for significant event, occasional/rare weekend cigarette or marijuana use).
- 16. Positive blood screen for hepatitis C virus antibody, hepatitis B virus core antibody, hepatitis B surface antigen, or human immunodeficiency virus (HIV) 1 and 2 antibodies (except subjects who test positive for hepatitis B surface antigen alone due to a hepatitis B vaccination).
- 17. Presence of chronic or active infection at Screening including positive result for active tuberculosis (TB) (ie positive QuantiFERON® test result without any prior history of active nor latent TB infection and without evidence of active infection) where the subject has not completed prophylactic treatment.
- 18. Any comorbidity that the Investigator believes is a contraindication to study participation. This includes, but is not limited to, any respiratory (eg, pulmonary fibrosis, eosinophilic granulomatosis with polyangiitis, allergic bronchopulmonary aspergillosis), cardiovascular, gastrointestinal, hematological, neurological, immunological, musculoskeletal, renal, infectious, neoplastic, or inflammatory condition that may place the safety of the subject at risk during the study, impact results of the study or their interpretation, or prevent subject from completing the study.

19. Comorbid asthma when:

- a) Forced expiratory volume (FEV₁) \leq 60% of predicted normal as assessed on Day 1 as defined by the Global Lung Initiative (GLI)
- b) An exacerbation requiring systemic (oral and/or parenteral) corticosteroid treatment or hospitalization (> 24 hours) for treatment of asthma within 3 months prior to Screening
- c) A daily dose higher than 1000 µg fluticasone or the equivalent of inhaled corticosteroids

- 20. Have any other physical, mental, or medical conditions that, in the opinion of the Investigator, makes study participation inadvisable or could confound study assessments.
- 21. Receipt of live attenuated vaccine within 4 weeks before Screening.
- 22. Planned surgery during the study or within 30 days before Screening.
- 23. History of malignancy within 5 years, except non-melanoma skin cancer that has been fully treated with no current active disease.
- 24. Initiation of allergen immunotherapy:
 - a) Within 12 weeks prior to Screening
 - b) Planned to begin therapy during the screening period
 - c) Planned to begin during the randomized treatment period

Subjects who started immunotherapy more than 12 weeks prior to Screening can continue the immunotherapy during the study providing dosing is at least 2 weeks prior to each dose of study drug.

- 25. Undergone any nasal surgery (eg, any procedure with excision of tissue) within 3 months before randomization (Day 1).
- 26. Evidence of drug/substance abuse that would pose a risk to subject safety, interfere with the conduct of the study, or affect the subject's ability to participate in or comply with the study protocol, including but not limited to evidence of misuse of addictive drugs, such as opioids, outside of prescribed medications for a medical condition.

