5.4 SCREEN FAILURES

Screen failures are defined as subjects who consent to participate in the clinical trial but are not subsequently randomly assigned to the study intervention or entered in the study. A minimal set of screen failure information is required to ensure transparent reporting of screen failure participants, to meet the Consolidated Standards of Reporting Trials (CONSORT) publishing requirements and to respond to queries from regulatory authorities. Minimal information includes demography, screen failure details, eligibility criteria, and any SAE.

Subjects who do not meet the criteria for participation in the study (screen failure) may be rescreened up to 2 more times during the enrollment period of the study. All requests for second rescreening must be discussed with the medical monitor and approved by the Sponsor.

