7.2 PARTICIPANT DISCONTINUATION/WITHDRAWAL FROM THE STUDY

Subjects are free to withdraw from participation in the study at any time upon request.

An Investigator must discontinue or withdraw a subject from the study and follow for safety for the following reasons:

- Any subject becomes pregnant or indicates they are planning to become pregnant during the study
- Any LFT abnormality that meets the following criteria require discontinuation:
 - If a subject has at any time post-initial dose an AST or ALT >5-8x ULN for more than 2 weeks, discontinue dosing; or
 - AST or ALT >8x ULN, irrespective of duration discontinue dosing; or
 - o Concurrent AST or ALT >3x ULN and total bilirubin >2x ULN discontinue dosing.

An Investigator may discontinue or withdraw a subject from the study for the following reasons:

- Significant study intervention noncompliance (eg, failure to follow study procedures or to keep follow-up appointments)
- If any clinical AE, laboratory abnormality, or other medical condition or situation occurs such that continued participation in the study would not be in the best interest of the subject
- Disease progression which requires discontinuation of the study intervention
- If the subject meets an exclusion criterion (either newly developed or not previously recognized) that precludes further study participation

If the subject withdraws consent and discontinues from the study, the Investigator will attempt to determine the reason for discontinuation and record the reason in the subject's study records and on the eCRF. If a subject withdraws consent because of an AE, that AE should be indicated as the reason for withdrawal. In the event of early discontinuation, the subject should be asked to return to the study center to complete the assessments specified in the ETV.

If at any time during the study, the investigator determines that it is not in the best interest of the subject to continue, the subject will be discontinued from participation. The Investigator can discontinue a subject at any time if medically necessary. Appropriate documentation in the subject's study record and eCRF regarding the reason for discontinuation must be completed. Prior to discontinuing a subject from study participation, the Investigator will discuss his/her intentions with the medical monitor or designee.

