10.1.6 DATA AND SAFETY MONITORING BOARD

A DSMB, or otherwise called Independent Data Monitoring Committee, will be set up, prior to the first subject being enrolled in the study, as an independent body to review accumulating data in the study. The DSMB is comprised of 3 independent clinicians (2 pulmonologists, 1 ENT specialist) and 1 independent statistician. Members of the DSMB will not be Investigators in the study, and will be free of any conflicts of interest with the Sponsor or study outcome.

The DSMB will periodically examine the safety data emerging from the study and provide its recommendations to the Sponsor. The roles and responsibilities of the DSMB, their operational procedures, and method of communication with Sponsor will be described in a separate DSMB charter.

The first DSMB meeting is expected to occur prior to the Investigators Meeting. A formal review of the accumulating data is planned for every quarter thereafter, unless an ad hoc meeting is required.

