10.2.2 AMENDMENT POLICY

Only the Sponsor may modify the protocol. Protocol amendments will be made after consultation between the Sponsor and the Investigator(s). Amendments must be approved by all applicable national and local committees including, but not limited to, the government regulatory authorities and/or regional IRB before implementation. The only exception is when an Investigator considers that a subject may be harmed and immediate action] is necessary. Under these circumstances, approval of the chairman of the IRB, or an authorized designee, must be sought immediately. The Investigator should inform the Sponsor, and the full IRB, no later than 5 working days after the emergency occurs.

Protocol-specified safety reporting requirements must be adhered to independent of any other variables. All amendments that have an impact on subject risk, the study objectives or that require revision of the informed consent document must be approved by the IRB before implementation. Administrative changes to the protocol and/or changes that do not impact subject safety, risk, or

comfort may be implemented prior to IRB approval if local institutional policy permits. A copy of the written approval of the IRB, which becomes part of the essential study documents file, must be given to the study monitor. Examples of amendments requiring such approval are:

- A significant change in the study design
- An increase in the number of invasive procedures to which subjects are exposed
- An addition or deletion of a test procedure

The PI at each study center must sign the Investigator's Agreement page of the amended protocol.

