- 15. Current smokers or former smokers with a smoking history of ≥ 10 pack-years [(number of cigarettes per day/20) × number of years smoked]. A former smoker is defined as a subject who quit smoking at least 2 months prior to Screening visit. This includes electronic cigarettes and vaping. Subjects who smoke medicinal marijuana can be enrolled at the investigator's discretion (conversion to edible forms of marijuana is preferred). Occasional smoking is permitted at the discretion of the investigator (e.g., cigar or pipe for significant event, occasional/rare weekend cigarette or marijuana use).
- 16. Positive blood screen for hepatitis C virus antibody, hepatitis B virus core antibody, hepatitis B surface antigen, or human immunodeficiency virus (HIV) 1 and 2 antibodies (except subjects who test positive for hepatitis B surface antigen alone due to a hepatitis B vaccination).
- 17. Presence of chronic or active infection at screening including positive result for active tuberculosis (TB) (i.e. positive QuantiFERON® test result without any prior history of active nor latent TB infection and without evidence of active infection) where the subject has not completed prophylactic treatment.
- 18. Any co-morbidity that the investigator believes is a contraindication to study participation. This includes, but is not limited to, any respiratory (e.g., pulmonary fibrosis, eosinophilic granulomatosis with polyangiitis, allergic bronchopulmonary aspergillosis), cardiovascular, gastrointestinal, hematological, neurological, immunological, musculoskeletal, renal, infectious, neoplastic, or inflammatory condition that may place the safety of the subject at risk during the study, impact results of the study or their interpretation, or prevent subject from completing the study.
- 19. Comorbid asthma when:
 - a) Forced expiratory volume (FEV₁) \leq 60% of predicted normal as assessed on Day 1 and defined by the Global Lung Initiative (GLI)
 - b) An exacerbation requiring systemic (oral and/or parenteral) corticosteroid treatment or hospitalization (> 24 hours) for treatment of asthma within 3 months prior to screening.
 - c) A daily dose higher than 1000 µg fluticasone or the equivalent of inhaled corticosteroids.
- 20. Have any other physical, mental, or medical condition that, in the opinion of the investigator, makes study participation inadvisable or could confound study assessments.
- 21. Receipt of live attenuated vaccine within 4 weeks before screening.

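### Exclusion 17 contradicts itself on tuberculosis and does not expressly exclude a QuantiFERON-positive subject with known, incompletely treated TB infection

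*Protocol*

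**What the plan says.** Criterion 17 in protocol section 5.2 has three parts:

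- An opening exclusion for chronic or active infection, with a positive result for active TB given as an included case.
- A parenthesis, introduced by *ie*, that explains the TB result as a positive QuantiFERON.
- A closing condition on prophylaxis.

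The parenthesis and the closing condition read "without any prior history of active nor latent TB infection and without evidence of active infection) where the subject has not completed prophylactic treatment". SAP section 3.5.2 repeats the definition ("test result without any prior history of active nor latent TB infection"), so the SAP does not correct it.

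Neighbouring criteria are built differently. Criterion 16 works by test result, "Positive blood screen for hepatitis C virus antibody, hepatitis B virus core antibody, hepatitis B surface antigen" or HIV antibodies, with no condition on history; its only exception concerns hepatitis B vaccination. Criterion 18 is discretionary: "Any comorbidity that the Investigator believes is a contraindication to study participation", with infectious conditions among its examples. Criterion 20 also rests on the investigator's opinion.

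The Schedule of Activities (protocol section 1.3) places the TB test at Screening only. Its footnote h and Table 1 in section 8.2.1 deal with retesting after an indeterminate result. Neither says how to classify a positive one.

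**The concern.** The criterion has two drafting faults. The explanation negates the term it explains, since what is called a result for active TB is described as a finding with no sign of active infection. The explanation also carries a history condition, so the only express rule for a positive QuantiFERON applies to subjects with no known past TB.

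The closing words suggest that uncompleted prophylaxis is the ground for exclusion. As written, that ground is express for a subject without TB history and a matter of interpretation for a subject with it. The synopsis expects about 25 sites, and they could settle the same case differently. What is at stake is subject safety at entry and uniform eligibility, because no further TB test is scheduled after Screening. No efficacy result is at stake.

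**Working it through.** No arithmetic applies; the point depends on no alpha, effect size, SD or sample size. The check is to take a subject with a positive QuantiFERON and follow criterion 17 clause by clause.

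1. **Evidence of active TB.** The subject is outside the parenthesis, which requires no such evidence. The opening words on active infection still exclude the subject, whatever the history.
2. **No evidence of active TB, no TB history, prophylaxis not completed.** The subject meets every element of the parenthesis and the closing condition, and is expressly excluded.
3. **No evidence of active TB, prophylaxis completed.** The closing condition is not met, so the TB wording does not exclude the subject.
4. **No evidence of active TB, known earlier active or latent TB, treatment or prophylaxis never started or not completed.** The history condition takes the subject outside the parenthesis, so there is no express exclusion. The subject is excluded only if the site regards the state as a chronic infection under the opening words, or acts under criterion 18 or 20.

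Cases 2 and 4 both involve a positive test and uncompleted preventive treatment, yet the express rule reaches only case 2. The documents give no reason for the difference.

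Other provisions that might close case 4:

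- **Retest rules (footnote h, Table 1).** These concern indeterminate results only.
- **Criterion 12.** It excludes systemic antibiotic treatment in the 4 weeks before Screening. If TB prophylaxis counts as such treatment (an assumption; the protocol does not say), it would catch a subject still taking it. It would not catch one who never started or who stopped earlier.
- **Monitoring (protocol section 10.1.7) and the listing of eligibility violations (SAP section 7.2).** Both check adherence to the criterion as written, so they inherit the ambiguity.
- **Section 7.2.** It permits withdrawal "If the subject meets an exclusion criterion (either newly developed or not previously recognized) that precludes further study participation", and requires discontinuation when continuing is not in the subject's best interest. Both act after enrolment.
- **Section 10.1.6.** "The DSMB will periodically examine the safety data emerging from the study", with formal review each quarter. This too acts after dosing has begun.

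The wording is current text: the SAP states that it is based on Amendment 3 and carries the same definition. It is therefore neither superseded nor damaged in extraction.

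**The case against.** The strongest reply is that the opening words already do the work. A case introduced by *including* does not narrow the general term before it, and a subject with a positive QuantiFERON and known, unfinished latent TB is naturally described as having a chronic infection. Criteria 18 and 20 stand behind that. Most of this holds: the open case is probably caught in practice. But *probably* is the difficulty, since a reader who takes the *ie* text as the definition of what counts for TB reaches the opposite answer.

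A second reply is that the history condition may be deliberate. The summary of changes for Amendment 2 records that the QuantiFERON requirements of exclusion 17 were updated, citing subject safety and investigator input, so known or previously managed TB may have been meant for separate handling. This stands as a possibility. It does not rescue the text, because no separate handling is stated, and it does not explain the contradiction over active infection.

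A third reply is proportion: an amendment, IRB approval and site signatures for a case that may never arise. This bears on timing and argues for combining the edit with another amendment.

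**Conclusion.** The concern holds as a minor subject-safety correction. Criterion 17 is self-contradictory, and a QuantiFERON-positive subject with known but untreated or incompletely treated TB infection and no evidence of active disease is not expressly excluded. The number of such subjects cannot be obtained from the documents and may be zero. There is no effect on power or on the randomised comparison.

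Three stronger readings are not supported:

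- A reader might infer that the criterion lets subjects with active TB into the trial. It does not; the opening words exclude them.
- A reader might infer that the history condition is plainly a mistake. The Amendment 2 entry leaves room for intent.
- A reader might infer that rewording would alter the status of exactly one type of subject. Accepting completed TB treatment as well as prophylaxis divides the open group, because a subject fully treated for earlier active TB, without ever having prophylaxis, remains eligible.

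The conclusion assumes that the protocol does not intend to dose a subject with a positive test and incomplete treatment, which the closing condition suggests but does not state for subjects with TB history.

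**What to change.** Keep the opening words of criterion 17 and replace the TB text after *including* with:

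> (a) evidence of active TB; or (b) a positive QuantiFERON result without evidence of active TB in a subject who has not completed appropriate TB treatment or prophylaxis, regardless of TB history.

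Make the same edit in SAP section 3.5.2, where it changes no analysis. Before adopting it, the sponsor should confirm that the history condition was not intended. If it was, the criterion should say how those subjects are to be handled.

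Subjects with prior TB who completed treatment remain eligible. A subject excluded under (b) "may be rescreened up to 2 more times during the enrollment period of the study" (section 5.4), so completing treatment could reopen entry while enrolment lasts.

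The cost is a short amendment. Section 10.2.2 requires IRB approval before implementation for "All amendments that have an impact on subject risk, the study objectives or that require revision of the informed consent document", and the principal investigator at each of the roughly 25 sites signs the amended protocol. No new test or visit is needed. Combine the edit with the next amendment if enrolment is still open; the documents do not give enrolment status. The new wording should apply from its approval. Subjects already randomised entered under the criterion then in force and should not be judged against the new one.
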